8.4.1.2 Adverse events requiring additional data collection

For some AEs additional data collection is required and specific event forms must be completed in the eCRF in addition to the AE form.

In case any of these events fulfil the criteria for a serious adverse event, please report accordingly, see Section [12](#).

Acute coronary syndrome

If an event of Acute Coronary Syndrome (ranging from unstable angina pectoris to myocardial infarction) is observed during the trial the following additional information must be reported if available on the acute coronary syndrome form:

- Duration of symptoms
- Changes in ECG
- Collection of cardiac biomarkers
- Cardiac imaging
- Cardiac stress testing
- Angiography
- Use of thrombolytic drugs
- Revascularisation procedures

Cerebrovascular events

If a cerebrovascular event (e.g. transient ischaemic attack (TIA), stroke, and haemorrhage) is observed during the trial the following additional information must be reported if available on the cerebrovascular event form:

- Type of event (e.g. TIA, Stroke)
- Contributing condition
- Neurologic signs and symptoms
- History of neurologic disease
- Imaging supporting the event
- Treatment given for the event

Neoplasm

All events of benign, pre-malignant/carcinoma in-situ and malignant neoplasm must be reported during the trial and the following additional information should be obtained if available as part of standard of care on the neoplasm form:

- Type of neoplasm
- Symptoms and laboratory results leading to identification of event
- Diagnostic imaging
- Pathological examination (outcome and staging)
- Treatment given for the event
- Participation in screening programs
- Relevant risk factors associated to the event

Events for adjudication

Severe hypoglycaemia or hypoglycaemic episodes reported as an SAE and all fatal events will be subject to external independent adjudication. For these AEs a (hypoglycaemia) Adjudication Form must be completed in the eCRF. For detailed information on event adjudication, please refer to Section [12.7.2](#).

8.4.2 Hypoglycaemic episodes

Plasma glucose should always be measured and recorded when a hypoglycaemic episode is suspected.

All plasma glucose values:

- ≤ 3.9 mmol/L (70 mg/dL) or
- > 3.9 mmol/L (70 mg/dL) occurring in conjunction with hypoglycaemic symptoms

should be reported in the diary according to the instructions below throughout the trial from visit 2 to the End of Trial visit (V56 or V95).

Upon onset of a hypoglycaemic episode the subject is recommended to measure plasma glucose every 15 minutes until the SMPG value is >3.9 mmol/L (70 mg/dL) and/or symptoms have been resolved in accordance to current guidelines²⁹.

A SMPG value ≤ 3.9 mmol/L (70 mg/dL) or hypoglycaemic symptoms must trigger a hypoglycaemic episode form to be completed by the subject. Repeated SMPG measurements and/or symptoms, occurring within a period of 60 min after onset on a hypoglycaemic episode, will by default be considered as one hypoglycaemic episode until a succeeding SMPG value is >3.9 mmol/L (70 mg/dL) and/or symptoms have been resolved and should be reported on one hypoglycaemic episode form. SMPG measurements ≤ 3.9 mmol/L (70 mg/dL) or hypoglycaemic symptoms after the 60 min period shall trigger the reporting of a new hypoglycaemia episode and prompt the subject to fill out a new hypoglycaemic episode form until a succeeding measurement is >3.9 mmol/L (70 mg/dL) and/or symptoms have been resolved.

In case of several low SMPG values within the 60 minutes interval, the lowest value is the one that will be reported as the SMPG value for the hypoglycaemic episode but the start time of the episode will remain as the time for the first SMPG value and/or symptom.

The record should include the following information:

- Start date and time of the hypoglycaemic episode
- The plasma glucose level before treating the episode (if available) and any follow up measurements
The lowest value measured during the hypoglycaemic episode will be reported as the plasma glucose value for the episode, the remaining values will be kept as source data in the diary.
- Whether the episode was symptomatic (Yes/No)
A hypoglycaemic episode starting without symptoms should be updated to symptomatic if the subject experiences symptoms later during the episode.
- Whether the subject was able to treat him/herself
If the severity of a hypoglycaemic episode aggravates, only one hypoglycaemic episode should be reported reflecting the most severe degree of hypoglycaemia.
- Date, time and dose of last trial product administration prior to the episode
- Date and time of last main meal (not including snacks) prior to the episode
- Whether the episode occurred in relation to physical activity
- Whether the episode related to a change in a pre-existing disease
- Any sign of fever and/or other acute disease
- Whether the subject was asleep when the episode occurred
 - If yes, whether the symptoms of the episode woke up the subject

The answer to the question: "Was the subject able to treat him/herself?" must be answered "No" for an episode requiring assistance of another person to actively administer carbohydrate, glucagon, or take other corrective actions. Plasma glucose concentrations may not be available during an event,

but neurological recovery following the return of plasma glucose to normal is considered sufficient evidence that the event was induced by a low plasma glucose concentration²⁹.

Oral carbohydrates must not be given if the subject is unconscious.

If the question "Was the subject able to treat him/herself?" is answered "No", the following information should be recorded by the subject:

- Who assisted in the treatment of the hypoglycaemic episode (i.e. medical person or non-medical person)?
- Where the treatment was administered (in clinic/emergency room/hospital or other. If the subject was treated in clinic/emergency room/hospital, whether they were transported in an ambulance or not)
- Type of treatment provided by another person (i.e. oral carbohydrates, glucagon, IV glucose or other)
- Were symptoms alleviated after administration of treatment?
- Factors contributing to the episode (i.e. physical activity, missed meal, diet change, medication error (i.e. overdose, mix-up between products, incorrect use of device), miscalculation of dose of anti-diabetic medication, other factors not listed or unknown)
- Did the subject experience seizure?
- Was the subject unconscious/comatose?
- Did the subject experience any of the following symptoms³⁰ (layman term used in the diary is specified in brackets if different from the protocol term)?
 - Autonomic: sweating, trembling, hunger or palpitations (rapid or irregular heart beat)
 - Neuroglycopenic: confusion, drowsiness, speech difficulty, visual disturbances, odd behaviour, impaired balance or incoordination (reduced ability to coordinate movement)
 - General malaise: headache or malaise (feeling discomfort/unease)
- Other symptoms.

The investigator must review the diary data for low SMPG values not reported as hypoglycaemic episodes. The subject must be questioned whether any of the low values were severe, i.e. whether the subject was able to self-treat or not. If the subject was not able to self-treat, it has to be reported as a severe hypoglycaemic episode.

All hypoglycaemic episodes must be transcribed into the eCRF during or following the contact. If obtained via phone and a discrepancy is later detected, the values in the eCRF must be corrected.

Low SMPG values for non-severe hypoglycaemic episodes not having a hypoglycaemic episode form completed within 7 days since the SMPG measurement should be reported on a hypoglycaemic episode form with as much information as possible. Novo Nordisk will not query for additional data except for the start date, SMPG value, if any symptoms were present and whether the subject was able to self-treat due to decreased validity of such data^{31,32}.

The subject must be re-trained in how to report hypoglycaemic episodes if the investigator identifies low SMPG values not reported as hypoglycaemic episodes.

If the hypoglycaemic episode fulfils the criteria for an SAE then an AE form, a safety information form and an adjudication form must also be filled in, see Section [12](#).

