- Factors contributing to the episode (i.e. physical activity, missed meal, diet change, medication error (i.e. overdose, mix-up between products, incorrect use of device), miscalculation of dose of anti-diabetic medication, other factors not listed or unknown)
- Did the subject experience seizure?
- Was the subject unconscious/comatose?
- Did the subject experience any of the following symptoms³⁰ (layman term used in the diary is specified in brackets if different from the protocol term)?
 - Autonomic: sweating, trembling, hunger or palpitations (rapid or irregular heart beat)
 - Neuroglycopenic: confusion, drowsiness, speech difficulty, visual disturbances, odd behaviour, impaired balance or incoordination (reduced ability to coordinate movement)
 - General malaise: headache or malaise (feeling discomfort/unease)
- Other symptoms.

The investigator must review the diary data for correct reporting of SMPGs and hypoglycaemic episodes. In case of incomplete or incorrect data in the diary, the subject must be questioned whether there have been any severe hypoglycaemic episodes since the last visit, i.e. any hypoglycaemic episodes where the subject was not able to self-treat. Any severe hypoglycaemic episodes must be reported.

In case a subject is not able to fill in the eDiary e.g. in case of a fatal event, the investigator will be allowed to report the hypoglycaemic episode in the eDiary web portal.

Low SMPG values for non-severe hypoglycaemic episodes not having a hypoglycaemic episode form completed within 7 days since the SMPG measurement should be reported on a hypoglycaemic episode form with as much information as possible. Novo Nordisk will not query for additional data except for the start date, SMPG value, if any symptoms were present and whether the subject was able to self-treat due to decreased validity of such data^{31, 32}.

The subject must be re-trained in how to report hypoglycaemic episodes if the investigator identifies unreported hypoglycaemic episodes.

If the hypoglycaemic episode fulfils the criteria for an SAE then an AE form, a safety information form and an adjudication form must also be filled in, see Section [12](#).

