All AEs will be screened to detect potential missed events for adjudication. If needed, the investigator will be requested to provide additional information such as an alternative aetiology, underlying cause(s) and/or clinical details.

Based on the information provided, the Event Adjudication supplier or Event Adjudication Committee can decide to have an AE adjudicated even if not initially reported as an event for adjudication by the investigator. If so, the investigator must complete the Adjudication form and upload source data, when they receive the request from Novo Nordisk or the Event Adjudication supplier.

EAC identified events:

During the review of source data, the EAC may identify additional events relevant for adjudication, not reported as for such by the investigator. In case an additional event is identified, the site will be informed and asked to consider reporting the event. If the site does not report the event, it may still be adjudicated.

For all events for adjudication, the source documentation should be anonymised by investigator according to the Event Adjudication Site Manual. Prior to submitting the source documentation to the EAC, the Event Adjudication supplier will ensure translation into English.

For each source document the investigator should specify/indicate on the adjudication form when/if the required documents will be available. If a document is unobtainable this needs to be specified. If no source data are available, a clinical narrative should be provided.

Protocol
Trial ID: NN1250-4252
UTN: U1111-1184-8175
EudraCT no.: 2016-002801-20

~~CONFIDENTIAL~~

Date:	11 November 2016	Novo Nordisk
Version:	2.0	
Status:	Final	
Page:	76 of 109	

For further details regarding event adjudication, please refer to the Event Adjudication Site Manual.

The assessment made by the event adjudication committee will be included in the clinical trial report as well as the assessments made by the investigator. However, the adjudication made by the event adjudication committee, given its independent analysis of each event, will be attributed with greater importance of the two.

13 Case report forms

Novo Nordisk will provide a system for the electronic case report forms (eCRF). This system and support services to the system will be provided by an external supplier.

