All SAEs will be screened to detect potential missed events for adjudication. If needed, the investigator will be requested to provide additional information such as an alternative aetiology, underlying cause(s) and/or clinical details.

Based on the information provided, the Event Adjudication supplier or Event Adjudication Committee can decide to have an SAE adjudicated even if not initially reported as an event for adjudication by the investigator. If so, the investigator must complete the Adjudication form and upload source data, when they receive the request from Novo Nordisk or the Event Adjudication supplier.

EAC identified events:

During the review of source data, the EAC may identify additional events relevant for adjudication, not reported as for such by the investigator. In case an additional event is identified, the site will be informed and asked to consider reporting the event. If the site does not report the event, it may still be adjudicated.

For all events for adjudication, the source documentation should be anonymised by investigator according to the Event Adjudication Site Manual. Prior to submitting the source documentation to the EAC, the Event Adjudication supplier will ensure translation into English.

For each source document the investigator should specify/indicate on the adjudication form when/if the required documents will be available. If a document is unobtainable this needs to be specified. If no source data are available, a clinical narrative should be provided.

For further details regarding event adjudication, please refer to the Event Adjudication Site Manual.

The assessment made by the event adjudication committee will be included in the clinical trial report as well as the assessments made by the investigator. However, the adjudication made by the event adjudication committee, given its independent analysis of each event, will be attributed with greater importance of the two.

13 Case report forms

Novo Nordisk will provide a system for the electronic case report forms (eCRF). This system and support services to the system will be provided by an external supplier.

The investigator must ensure that all relevant questions are answered, and that no empty data field exists. If a test or an assessment has not been done and will not be available, or if the question is irrelevant (e.g. is not applicable), indicate this according to the data entry instructions.

The following will be provided as paper CRFs:

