Data collected after premature treatment discontinuation will not be used when addressing the ontreatment estimand. With the aim of comparing a safety endpoint this estimand is considered the most relevant as it compares the occurrence of a safety endpoint that is caused by the drug during exposure to the drug. The confirmatory endpoints will additionally be investigated with a ITT estimand.

The secondary estimand is the treatment difference between IDeg and IGlar 300 U/mL regardless of whether subjects adhered to the randomised treatment throughout the trial, that is an ITT estimand. For this ITT estimand, data collected after premature discontinuation will be used.

In accordance with guidance⁹ endpoints will be assessed at frequent visits and also for subjects who prematurely discontinue treatment. When an assessment is planned at randomisation visit, this value will be used as baseline value. If this value is missing the last recorded value before randomisation visit will be used. For assessments planned only at screening, the screening values will be used as baseline. If this value is missing, the first recorded visit after screening, but no later than the day of randomisation, will be used.

For patients not initiating maintenance period 2 on treatment a summary table of reasons for treatment discontinuation will be reported.

The severe hypoglycaemia episodes included in the statistical analysis are all events adjudicated with the outcome severe hypoglycaemia.

Laboratory values below the lower limit of quantification (LLOQ) will be set to ½LLOQ. Laboratory values above the upper limit of quantification (ULOQ) will be set to ULOQ+1.

The primary and secondary endpoints will be tested in a hierarchical order using the on-treatment estimand to control the family wise Type I error in the strong sense. Presentation of results from a statistical analysis will include the estimated treatment means as well as estimated mean treatment difference (or ratio) together with the two-sided 95% confidence interval and corresponding two-sided p-value.

In the statistical models explanatory factors will be categorized as follows:

- 1. Treatment: IDeg, IGlar 300 U/mL
- **2.** Pre-trial 0 OADs, 1OAD, \geq 2 OADs
- 3. Region: Europe, North America
- 4. Sex: male, female
- 5. Dosing time: morning, evening

2.2 **Power calculation**

The power is based on the primary objective and the primary endpoint, number of hypoglycaemic episodes during maintenance treatment.

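### In protocol version 3.0 the only site question specific to severe hypoglycaemia depends on a recorded low glucose value, and the screen for missed adjudication events covers only SAEs

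*Protocol*

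**What the plan says.** All references are to protocol version 3.0 unless stated. It governs maintenance 2, the period for every confirmatory hypoglycaemia endpoint.

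- **Site review (8.4.2).** "The investigator must review the diary data for low SMPG values not reported as hypoglycaemic episodes". The severity question follows from that review: "The subject must be questioned whether any of the low values were severe, i.e. whether the subject was able to self-treat or not". A value that the subject could not self-treat is then reported as a severe episode.
- **Definition of severe (8.4.2, 17.7).** The criterion is that another person had to give active help. The text accepts that a reading may be missing: "Plasma glucose concentrations may not be available during an event".
- **Missed-event screen (12.7.2).** "All SAEs will be screened to detect potential missed events for adjudication".
- **Adjudication scope (Tables 12-1 and 12-2, 12.7.2).** Severe episodes are in scope whether or not they are serious: the adjudication form is required for every severe episode, and the AE and safety information forms are added when it is also an SAE. Section 12.1.2 does not list severe hypoglycaemia among the events that are always serious.
- **Analysis (SAP 2.1).** "The severe hypoglycaemia episodes included in the statistical analysis are all events adjudicated with the outcome severe hypoglycaemia".
- **General routes.** Hypoglycaemic episodes are a listed item at every maintenance 2 site visit (Table 2-2) and phone contact (Table 2-4). An open question about problems since the last contact is mandatory each time (8.4.1, 12.2). Symptoms alone oblige the subject to complete an episode form (8.4.2). Monitors compare medical records and diaries with the eCRF (section 14). The adjudication committee may also find events itself: "During the review of source data, the EAC may identify additional events relevant for adjudication, not reported as for such by the investigator".

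**The concern.** The trigger for the question does not match the definition of the event. Severity turns on whether help was needed, but the site asks about help only when the diary holds a low reading. Take a subject who becomes confused at night, is given juice by a relative, has no meter reading and completes no form. No low value exists, so the scripted question does not arise. If the episode was not serious, the SAE screen does not reach it either. If it was recorded as a non-serious AE under another term, such as confusion or a fall, nothing in 12.7.2 requires that record to be checked for adjudication.

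Only episodes adjudicated as severe are analysed as severe, so an episode that never reaches the committee drops out of the third confirmatory endpoint, where few events are expected. It may also be unknown to the investigator, who reviews the insulin dose at each weekly contact.

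**Working it through.** **1. The routes, set against such an episode** (severe, not serious, no glucose value, no form completed)

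| Route | Reaches it? |
|---|---|
| Severity question, 8.4.2 | No: needs a recorded low value |
| Missed-event screen, 12.7.2 | No: SAEs only |
| Hypoglycaemia item at each contact, Tables 2-2 and 2-4 | Possibly: it refers to 8.4.2, which scripts no question on needing help without a low value |
| Open AE question, 8.4.1 and 12.2 | Possibly: depends on the subject volunteering it |
| Symptom-triggered form, 8.4.2 | Only if the subject recognises and records it |
| Monitor review, section 14 | Only if a medical record or diary mentions it |
| Committee's source review, 12.7.2 | Mainly subjects whose data it already holds |

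Several routes could bring the episode to light. None asks specifically whether help was needed.

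**2. Inputs** (17.2, Table 17-2; repeated in SAP 2.2): 805 per arm; IDeg severe rate 0.03 per patient-year; true ratio 0.6, adjusted ratio 0.624; dispersion 3.1; one-sided 2.5%. Period: 36 weeks, T = 36/52 = 0.692 years.

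**3. Expected severe episodes**
- IDeg: 805 × 0.03 × 0.692 = 16.7
- IGlar: 16.7 / 0.624 = 26.8 (27.9 with the unadjusted 0.6)

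**4. Reproducing the stated power.** For a negative binomial log rate ratio, SE = √[(1/m₁ + 1/m₂ + 2 × 3.1)/805], with m₁ = 0.03 × 0.692 = 0.02077 and m₂ = m₁/0.624 = 0.03328.
- SE = √[(48.15 + 30.04 + 6.2)/805] = 0.324
- Power = Φ(|ln 0.624|/0.324 − 1.96) = Φ(1.457 − 1.96) = 30.7%, against 31% printed

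The same formula gives 78.6% for the primary endpoint (79% printed) and 81.9% for the nocturnal endpoint (82% printed).

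**5. Illustration of loss.** The documents give no missed fraction. The table assumes equal loss in both arms, so m₁ and m₂ shrink by the same factor.

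| Missed (assumed) | Expected episodes, IDeg / IGlar | Power |
|---|---|---|
| 0% | 16.7 / 26.8 | 30.7% |
| 10% | 15.0 / 24.1 | 28.3% |
| 20% | 13.4 / 21.4 | 25.9% |
| 30% | 11.7 / 18.8 | 23.3% |

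**6. Primary endpoint.** Severe episodes are 0.03/1.8 = 1.7% of the assumed IDeg rate. With half of them missed, the rate is 1.8 − 0.015 = 1.785 and power is still 78.6%.

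**The case against.** The strongest reply is that the collection route exists. Hypoglycaemia is on the agenda at every maintenance 2 contact, the AE question is mandatory, and section 12.1.1 states that non-serious hypoglycaemia is an AE, so that question covers it. Symptoms without a reading must lead to a form, and the form asks who assisted. For the episode to be lost, the subject must leave the form uncompleted and also say nothing at the next contact. This is ordinary under-reporting, which any self-reported endpoint carries. That stands, and it rules out a reading that a reader might otherwise take: that these episodes are never sought, or that the open AE question is the only general prompt.

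It is also fair that version 2.0 was not a routine safeguard. Its question, "the subject must be questioned whether there have been any severe hypoglycaemic episodes since the last visit", applied only when diary data were incomplete or incorrect. Its screen was wider, though: "All AEs will be screened to detect potential missed events for adjudication". It shows that an AE-wide screen was once planned for this trial, not that the present text is an error.

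Against the AE-wide screen, 12.1.1 puts non-serious hypoglycaemia on the episode form instead of an AE form. An episode reported nowhere leaves no AE record to search. That also stands: the wider screen catches only episodes filed under other AE terms.

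Two further inferences are tempting. One is that the primary endpoint is compromised; step 6 shows that it is not. The other is that open-label reporting biases the comparison. Arithmetically, 20% missed in one arm only would move 0.624 to 0.50 (0.624 × 0.8, missed on IDeg) or 0.78 (0.624/0.8, missed on IGlar). Nothing in the documents indicates that capture differs by arm, and a question answered by the subject would not necessarily remove such a difference.

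What the reply does not answer is the mismatch itself: needing help defines the event, yet the one question about help is tied to a glucose value.

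**Conclusion.** The point holds as a gap in specific ascertainment. A severe, non-serious episode without a recorded low value can surface through general routes, but no scripted site question asks about it, and one filed only under another non-serious AE term is not screened for adjudication.

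The statistical consequence falls on the third confirmatory endpoint. With about 17 and 27 episodes expected, each missed IDeg episode is about 6% of that arm's count (1/16.7). Power falls from 30.7% to between 28.3% and 23.3% for assumed equal losses of 10% to 30%. This rests on the plan's own rate, ratio and dispersion and on loss fractions that the documents do not supply. Since this endpoint is last in the testing order and already at 31% power, the change to the confirmatory strategy is small. The gain in complete safety information matters at least as much. It is a cheap improvement worth making, not a flaw in the primary analysis.

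**What to change.** **Section 8.4.2.** At every scheduled site visit and phone contact, ask each subject whether any episode since the last contact needed another person's help, whether or not a low value or diary entry exists. Record yes or no in the eCRF. Each yes leads to an episode form and an adjudication form. Relatives need not be interviewed.

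**Section 12.7.2.** Extend the missed-event screen from SAEs to all AEs, for example by a term search of the AE data already collected, and state that this finds only episodes recorded under other AE terms.

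**Cost.** One question and one eCRF field at contacts that already take place, a term search, and a few more adjudication packages. The endpoint definitions, the adjudication criteria and the analysis model are unchanged.
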